### **6.3. Analysis Populations**

Analysis populations defined in this section pertain to patients enrolled in the 402-C-1803 study.

#### **6.3.1. Safety Population**

The safety population includes all patients who received at least 1 dose of bardoxolone methyl in 402-C-1803 study. The safety population is used for evaluation of safety variables.

### **6.3.2. 402-C-1603 to 402-C-1803 Safety Population**

The 402-C-1603 to 402-C-1803 safety population includes all patients previously enrolled in 402-C-1603 study who received at least 1 dose of bardoxolone methyl in 402-C-1803 study.

### **6.3.3. 402-C-1808 to 402-C-1803 Safety Population**

The 402-C-1808 to 402-C-1803 safety population includes all patients previously enrolled in 402-C-1808 study who received at least 1 dose of bardoxolone methyl in 402-C-1803 study.

Subgroup analyses will not be conducted due to termination of the bardoxolone methyl program. However, summaries based on the parent studies (402-C-1808 and 402-C-1603) will be provided along with a pooled analysis.

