5.1.2.7. Growth and Development (Weight and Height) in Adolescents

In study 402-C-1603 (CARDINAL) phase 3, due to the small number of patients and baseline differences in mean height and weight (placebo vs. bardoxolone methyl treated), a firm conclusion regarding effect on height and weight cannot be derived.

In study 402-C-1603, a total of 23 adolescent patients (ages 12-17 years) with Alport syndrome were enrolled, where 11 and 12 were randomized to bardoxolone methyl and placebo, respectively. In bardoxolone methyl treated adolescents, both weight and height at baseline were relatively higher than placebo treated adolescents. Bardoxolone methyl treated patients had a mean baseline weight of 65.50 kg (SD 10.193, median 63.90 kg, min/max 52.5/81.3 kg), while placebo treated adolescents had a mean baseline weight of 57.79 kg (SD 16.020, median 59.80 kg, min/max 29.5/76.3 kg). A change from baseline using the last on treatment value available for weight showed a mean weight decrease of -1.41 kg (SD 5.260, median -2.30 kg, min/max -10.9 to 6.8 kg) for bardoxolone methyl treated adolescents and a mean weight increase of +2.26 kg (SD 4.153, median +2.25 kg, min/max -5.7 to +8.2 kg) for placebo treated adolescents.

Bardoxolone methyl treated adolescents at baseline had a mean height of 171.7 cm (SD 5.90, median 172.0 cm, min/max 165/183 cm), while placebo treated adolescents had a mean height of 166.3 cm (SD 14.94, median 169.5 cm, min/max 136/186 cm). A change from baseline using the last on treatment value available showed a mean height increase of +1.1 cm (SD 1.13, median +1.0 cm, min/max 0 to 3 cm) for bardoxolone methyl treated adolescents, compared with a mean height increase of +2.4cm (SD 3.65, median 0.6 cm, min/max -1 to +11cm) for placebo treated adolescents.

Bardoxolone methyl treated adolescents at baseline had a mean body mass index (BMI) of 22.1 kg/m² (SD 2.11, median 22.3 kg/m², min/max 19/25 kg/m²), while placebo treated adolescents at baseline had a mean BMI of 20.5 kg/m² (SD 3.63, median 20.3 kg/m², min/max

16/26 kg/m²). Overall, in bardoxolone methyl treated adolescents, BMI changes from baseline to last value on treatment showed a mean decrease of -0.5 kg/m² (SD 1.40, median -0.8 kg/m², min/max -3/+2 kg/m²), compared with a mean BMI increase in placebo treated adolescents of 0.3 kg/m² (SD 1.15, median 0.3 kg/m², min/max -2/+2 kg/m²).

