Overall, no other concerning differences in the safety profile were identified in patients 12 to < 18 years of age compared to adult patients randomized to receive bardoxolone methyl (total: n=77; adults: n=66) or to receive placebo (total: n=80; adults: n=68).

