9.1.10. Monitoring Growth and Sexual Development in Adolescents

Growth and sexual development will be assessed through an evaluation of height, weight, and Tanner Staging. See the Study Reference Manual for details on the Tanner staging.

Body weight should be measured daily by patients/caregivers using a provided weighing scale. Weight and height will also be measured at all site visits, as outlined in Section 9.9.4 and

Section 9.9.5. Patients should be instructed to inform the site if there is an observed weight loss of more than 3 pounds (1.4 kg) in between clinic visits (Section 9.1.1).

The medical monitor will routinely evaluate both weight and height entered into the clinical database of adolescents and will inform the investigator to initiate further evaluation if there is a weight loss of $\geq 5\%$ or lack of expected growth per growth charts.

Sexual maturity will be assessed by the investigator using Tanner Staging. If any abnormal patterns of sexual maturity are identified on evaluation of Tanner Staging, the medical monitor should be notified for additional discussion.

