### **4.3. Sample Size Considerations**

The 402-C-1803 study is not powered to show efficacy or safety effects, and there is no placebo comparator in this open-label trial. Patient numbers are determined by those who are participating (or who have previously participated) in a qualifying clinical study with bardoxolone methyl and meet eligibility criteria.

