### **8.5. Vital Signs**

Vital signs assessments include systolic blood pressure (mmHg) and diastolic blood pressure (mmHg), body temperature ( $^{\circ}$ C), heart rate (bpm), height (cm), weight (kg), and body mass index (kg/m^2). Vital signs are summarized at baseline and at each time point (Section 6.5.4) along with the change from baseline by treatment analysis group (Section 4.5). Line graphs of change from baseline over time for blood pressure are plotted.

All data are listed.

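### Adolescent growth and sexual development are to be assessed, but the SAP pools height, weight and BMI change with adults and plans no output for Tanner stage

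*SAP*

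**What the plan says.** Protocol 5.1.2.7 reviews the CARDINAL phase 3 adolescents and concludes that "a firm conclusion regarding effect on height and weight cannot be derived", citing small numbers and baseline differences between arms. Protocol 9.1.10 then states: "Growth and sexual development will be assessed through an evaluation of height, weight, and Tanner Staging". It describes patient-level steps. The medical monitor reviews the recorded weights and heights and prompts further evaluation if weight falls by 5% or more or growth lags the growth charts. Abnormal Tanner patterns are also taken to the medical monitor.

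Protocol Table 5 and 9.9.20 schedule Tanner staging at Day 1, at each 24-weekly visit and at the end of study, for patients who enter from FALCON as adolescents. Protocol 12.2.1 lists height and weight among the safety variables. Tanner stage is not listed there, nor in the endpoints (6.2).

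SAP 8.5 treats "height (cm), weight (kg), and body mass index" as vital signs, summarized with change from baseline by treatment analysis group and listed by patient. SAP 8.5.1 adds one weight threshold, a gain of 2.3 kg or more. There is no threshold for loss. SAP 6.3.3 says: "Subgroup analyses will not be conducted due to termination of the bardoxolone methyl program". It keeps only summaries by parent study and pooled. The <18/≥18 category appears in SAP 7.4 as a baseline characteristic and is not used for any outcome. Tanner stage appears in the SAP only in the schedule of assessments and its footnote. SAP section 2 gives the SAP precedence over the protocol on planned analyses.

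**The concern.** Adults are not expected to gain height and adolescents are. A mean height change over both therefore depends on how many adolescents are in the group as well as on how much they grew. The weight and BMI means are legitimate summaries of the whole cohort, but a change confined to a small adolescent fraction is hard to see in them. The retained split by parent study does not help, because patients under 18 may enter from both CARDINAL and FALCON.

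For Tanner stage the gap is complete: minors are examined repeatedly and no table, figure or listing of the results is specified. The general SAP rule on listings (section 6) covers data that support tables and figures, so it does not clearly reach Tanner data either. The stated reason for dropping subgroups is the end of the program. SAP section 2 attributes that to efficacy results in another trial, not to any safety question having been resolved.

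**Working it through.** **The plan's own count.** Protocol 5.1.2.7 gives "a total of 23 adolescent patients (ages 12-17 years) with Alport syndrome were enrolled, where 11 and 12 were randomized", and also "bardoxolone methyl (total: n=77; adults: n=66) or to receive placebo (total: n=80; adults: n=68". From the second: 77 − 66 = 11 and 80 − 68 = 12, together 23, which agrees with the first. The adolescent share of CARDINAL phase 3 is 23/(77 + 80) = 23/157 = 14.6%.

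**Parent-trial differences, as background.** For bardoxolone methyl (n = 11) the protocol gives a "mean weight decrease of -1.41 kg (SD 5.260, median -2.30 kg, min/max -10.9 to 6.8 kg" range. For placebo (n = 12) the mean weight change is +2.26 kg (SD 4.153). Height change is +1.1 cm (SD 1.13) against +2.4 cm (SD 3.65). With SE = sqrt(SD1²/n1 + SD2²/n2) and Welch degrees of freedom:

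- Weight: −1.41 − 2.26 = −3.67 kg; SE = sqrt(5.260²/11 + 4.153²/12) = 1.99; 95% CI −7.83 to 0.49.
- Height: 1.1 − 2.4 = −1.3 cm; SE = sqrt(1.13²/11 + 3.65²/12) = 1.11; 95% CI −3.69 to 1.09.

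Both intervals include zero, which fits the protocol's statement that no firm conclusion is possible.

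**What pooling does.** With adolescent share p, pooled mean = p × adolescent mean + (1 − p) × adult mean. A departure d confined to adolescents moves the pooled mean by p × d. The documents do not give p for EAGLE, so I assume 5% to 20%. Parent-study eligibility assessments fall at Week 100 or 108, so some parent-trial adolescents will be adults at EAGLE entry.

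| Assumed p | 3.67 kg shows as | 1.3 cm shows as |
|---|---|---|
| 5% | 0.18 kg | 0.07 cm |
| 14.6% | 0.54 kg | 0.19 cm |
| 20% | 0.73 kg | 0.26 cm |

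For height the level itself is also hard to interpret. If adults change by 0 cm (assumption), an adolescent mean gain of 1.1 cm appears as 0.05 × 1.1 = 0.06 cm at p = 5% and 0.20 × 1.1 = 0.22 cm at p = 20%. The same growth gives a fourfold range, set only by the age mix.

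**What a separate adolescent table could deliver.** The 95% half-width is t × SD/sqrt(n). EAGLE adolescent numbers are not given. Protocol 7.3.4 mentions only about 20 treated Alport adolescents across CARDINAL and EAGLE, so I assume n = 10 to 25.

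- Weight, SD 5.26: ±3.8 kg (n = 10) to ±2.2 kg (n = 25).
- Height, SD 1.13: ±0.8 to ±0.5 cm.
- Height, SD 3.65: ±2.6 to ±1.5 cm.

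Such a table would describe adolescent growth with modest precision. It would not estimate a drug effect.

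**The case against.** The strongest defence is that growth monitoring under protocol 9.1.10 works patient by patient through the medical monitor, that no objective or endpoint concerns growth, and that the SAP discloses its dropped subgroups and the reason. For perhaps 20 patients, individual trajectories in a listing may be more useful than means. Raw means in centimetres and kilograms would still mix 12- and 17-year-olds. The SAP also says: "The 402-C-1803 study is not powered to show efficacy or safety effects, and there is no placebo comparator in this open-label trial".

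Much of this stands, and it rules out several stronger readings that a reader might infer:

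- *The parent trial already shows impaired growth.* It does not. The intervals include zero, and median height change runs the other way (+1.0 cm on bardoxolone methyl, +0.6 cm on placebo). The arms also differed at baseline (mean height 171.7 against 166.3 cm; minimum 165 against 136 cm).
- *EAGLE could confirm or exclude the −3.67 kg difference.* It cannot. That is a contrast with placebo, and every EAGLE patient receives the drug.
- *The SAP makes an adolescent change in height or weight undetectable.* It does not, because SAP 8.5 lists these data by patient.
- *The pooled weight and BMI means are meaningless.* They are not. Weight is an endpoint for all patients, and weight loss on the drug is described in adults too (protocol 5.1.2.4). The criticism applies in full only to height.
- *Omitting Tanner stage breaks an endpoint commitment.* It does not. Tanner stage is neither an endpoint nor a listed safety variable, and only adolescents from FALCON are staged.
- *The data were collected to answer the question left open by CARDINAL.* The protocol words the purpose as monitoring and assessment and does not make that link.

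What the defence does not supply is any summary in which adolescent growth can be read, or any output at all for Tanner stage.

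**Conclusion.** The point holds in a limited form. The protocol says adolescent growth and sexual development will be assessed, and it makes height and weight safety variables. The SAP's planned summaries do not show growth in adolescents, and Tanner data have no planned output. The all-ages height mean is uninformative about growth. The all-ages weight and BMI means are valid but dilute an adolescent-only change to between one twentieth and one fifth of its size under the assumed shares.

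This is a reporting gap worth closing before the final analysis. It does not threaten the study's conclusions. The absence of the outputs rests on the documents alone. The size of the dilution rests on the assumed adolescent share and on adults being unaffected.

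**What to change.** Write a single exception to SAP 6.3.3:

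- Present the planned height, weight and BMI change summaries by age at EAGLE consent (<18, ≥18), using the category in SAP 7.4 and stating that the EAGLE consent date applies.
- Preferably add age- and sex-standardized height, weight and BMI for adolescents, naming the growth reference, and the number of adolescents with weight loss of 5% or more from Day 1. These follow the yardsticks in protocol 9.1.10.
- Flag adolescents in the height and weight listing.
- Add a Tanner listing by visit and a Day 1 to last-visit shift table for FALCON adolescents.

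No new data, testing or other subgroup work is needed. The cost is a few more pages of tables, since the summaries repeat by visit, treatment analysis group and population. Restricting the adolescent tables to the 24-weekly visits would limit this. Numbers will be small and there is no comparator, so the text should say that the output is descriptive and cannot settle causation.

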## **6.4. Baseline Definition**

The last measurement on or prior to the date of first study drug administration is considered the 402-C-1803 Day 1 measurement for the calculation of baseline. If baseline is missing, the last available value in prior qualified studies will be used as baseline.

## **6.5. Derived and Transformed Data**

### **6.5.1. Baseline Age**

Subject's age in years is the age collected at 402-C-1803 Day 1.

### **6.5.2. Study Day**

Study day is the day relative to the date of first study drug kit dispensation in 402-C-1803, which may precede the date of first dose of study drug.

Assessments that occur after 402-C-1803 study drug dispensation, but on or before the date of first study drug administration are considered to occur on study Day 1.

For visits (or events) after the date of drug dispensing, day is calculated as:

- Study day = visit (or event) date - date of drug dispense + 1

For visits (or events) before the date of drug dispensing, day is calculated as:

- Study day = visit (or event) date - date of drug dispense

For listings (such as for AEs) the quantity 'days since first (or last dose)' is defined as:

- Days since first dose = event date – date of first dose + 1
- Days since last dose = visit (or event) date - date of last dose

For summaries that present distribution of time expressed in weeks and months, weeks will be defined as days divided by 7 and months as days divided by 30.4.

### **6.5.3. Change from Baseline**

Change from baseline is calculated as the result minus baseline, using the baseline value (Section 6.4) and the result assessed closest to the target study day for each analysis visit (Section 6.5.4).

#### 6.5.4. Visit Windows

**Table 2: Visit Window (Days)**

Analysis Visit	Label	Target Study Day	Analysis Window
0	Day 1	1	1
1	Week 1	7	$2 \leq \text{Study Day} \leq 10$
2	Week 2	14	$11 \leq \text{Study Day} \leq 21$
4	Week 4	28	$22 \leq \text{Study Day} \leq 35$
6	Week 6	42	$36 \leq \text{Study Day} \leq 49$
8	Week 8	56	$50 \leq \text{Study Day} \leq 70$
12	Week 12	84	$71 \leq \text{Study Day} \leq 126$
24	Week 24	168	$127 \leq \text{Study Day} \leq 210$
48	Week 48	336	$308 \leq \text{Study Day} \leq 364$
72	Week 72	504	$476 \leq \text{Study Day} \leq 532$
96	Week 96	672	$644 \leq \text{Study Day} \leq 700$
120, 144, etc.	Week 120, Week 144, Every 24 Weeks Thereafter	Analysis Visit $\times$ 7	$([\text{Analysis Visit} \times 7] - 28) \leq \text{Study Day} \leq ([\text{Analysis Visit} \times 7] + 28)$
FU	Follow-up	28 days after last dose	$14 \leq \text{Days after last dose}^a \leq 35$

a For safety analyses, last dose for patients completing the treatment or permanently discontinuing study drug that occur on the date of last dose or less than 14 days after last dose are considered on treatment.

The safety follow-up is based on days since last dose. If more than one assessment exists during the follow-up after last dose, the one closest to 28 days following the date of the last study drug administration is used for analysis and summary.

If a parameter is assessed or measured more than once within a visit window, the one that is closest to the protocol-scheduled time point (or target study day) is used for the purposes of data analysis and summary. If two assessments are equidistant from a target study day, the earlier assessment is used. If the visit used for analysis includes two assessments on the same day, the average of assessments will be used for non-laboratory parameters. For laboratory parameters, if both an original and retest result are available in the laboratory dataset, the original result will be used and the second (ie, “retested”) result will be ignored. Records from visits not closest to the target study day, and therefore not used in analyses, are presented in by-subject data listings.

#### 6.5.5. Laboratory Evaluations

Any laboratory assessments less than the lower limit of detection (LLD) are imputed as LLD/2. If no LLD is available, then the imputed value is the minimum numeric value listed divided by 2 (eg,

< 25 is 25/2=12.5). Laboratory assessments above the upper limit of detection are imputed as the upper limit of detection. If the lab result is qualitative but presented as > X, then the value X is used in the analysis.

### 6.5.6. Estimated Glomerular Filtration Rate

The formula used to calculate estimated glomerular filtration rate (eGFR) is based on the patient's age at the date of 402-C-1803 consent. The formula will not change throughout the study. However, note that the formula used in the prior study may be different if the patient was < 18 in prior study and at least 18 in 402-C-1803. The Chronic Kidney Disease - Epidemiology Collaboration equation is used for adult patients (age at consent at least 18 years):

- $eGFR \text{ (mL/min/1.73 m}^2\text{)} = 141 \times \min(S_{cr}/\kappa, 1)^\alpha \times \max(S_{cr}/\kappa, 1)^{-1.209} \times 0.993^{\text{Age}} \times 1.018 \text{ [if female]} \times 1.159 \text{ [if black]}$

The Bedside Schwartz equation is used for pediatric patients (age at consent of 12 to 17):

- $eGFR \text{ (mL/min/1.73 m}^2\text{)} = (0.41 \times \text{Height in cm}) / S_{cr}$

where  $S_{cr}$  is serum creatinine (mg/dL),  $\kappa$  is 0.7 for females or 0.9 for males, and  $\alpha$  is -0.329 for females or -0.411 for males. Min indicates the minimum of  $S_{cr}/\kappa$  and 1, and max indicates the maximum of  $S_{cr}/\kappa$  and 1. *Age* indicates age at time of serum creatinine collection. *Height* indicates height at time of serum creatinine collection. Estimated glomerular filtration rate (eGFR) will not be calculated by the central lab.

### 6.5.7. Urine Albumin to Creatinine Ratio (ACR)

Albumin/creatinine ratio is provided in the central laboratory database as the ratio of urine albumin to urine creatinine from the first morning void (FMV) urine collection. The ACR value is reported in the central laboratory database as missing when the FMV urine albumin result is < LLD. Urine albumin results < LLD and the corresponding ACR missing values is imputed as follows:

- If urine albumin result = < LLD, then
  - Imputed urine albumin result (mg/dL) = LLD/2
  - Imputed ACR (mg/g) = (imputed urine albumin result in mg/dL) / [(urine creatinine in mg/dL) / 1000]

The ACR results are log-transformed for analysis to produce data that are more normally distributed. Any imputed ACR result where ACR=0 is considered to be 0.1 mg/g for purposes of calculating the geometric mean.

#### 6.5.7.1. Baseline Urine Albumin to Creatinine Ratio Categorical Status

Baseline ACR status will also be grouped by the following categories using baseline ACR:

- < 30 mg/g
- 30 mg/g ≤ ACR ≤ 300 mg/g
- 300 mg/g < ACR ≤ 1000 mg/g
- 1000 mg/g < ACR ≤ 3500 mg/g

- $ACR > 3500$  mg/g

#### **6.5.7.2. ACR Category used in Stratification**

The ACR category used for stratification with the following categories:

- $ACR \leq 300$  mg/g
- $ACR > 300$  mg/g

#### **6.5.8. Natural log (ACR)/eGFR**

To evaluate ACR after adjusting for filtration rate,  $\ln(ACR)/eGFR$  (Section 6.5.7 and Section 6.5.6) is calculated.

### **6.6. Handling of Missing Data**

#### **6.6.1. Missing Endpoints**

Missing data are not imputed.

#### **6.6.2. Missing Start and Stop Dates for Prior and Concomitant Medication**

Missing start dates for concomitant medications are not imputed.

Concomitant medications with incomplete end dates are considered concomitant medications if:

- Day and month are missing, and the year is equal to or after the year of the first date of study drug administration;
- Day is missing and the year is after the year of the first date of study drug administration;
- Day is missing and the year is equal to the year of the first date of study drug administration and the month is equal to or after the month of the first date of study drug administration; or
- Year is missing.

#### **6.6.3. Missing Start and Stop Dates for Adverse Events**

Treatment-emergent adverse events (TEAEs) are events that either:

- Had a date of onset on or after the date of the first dose of study drug and not more than 30 days after the date of the last dose of study drug, or
- Had no recorded date of onset with a stop date after the first dose of study drug, or
- Had no recorded date of onset or stop date.

Adverse events with incomplete start dates are considered after the date of first dose if:

- Day and month are missing, and the year is equal to or after the year of the first date of study drug administration;
- Day is missing and the year is after the year of the first date of study drug administration;

- Day is missing and the year is equal to the year of the first date of study drug administration and the month is equal to or after the month of the first date of study drug administration; or
- Year is missing.

Adverse events with incomplete start dates are considered on or within 30 days of last dose, if:

- Day and month are missing, and the year is equal to or before the year of the date of last dose of study drug plus 30 days;
- Day is missing and the year is equal to or before the year of the date of last dose of study drug plus 30 days, and month is equal to or before the month of the date of last dose of study drug plus 30 days;
- Year is missing.

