### 7.1. Subject Disposition

A disposition summary includes the number and percentage of patients in the following categories:

- Patients with prior participation in 402-C-1603 phase 2
- Patients with prior participation in 402-C-1603 phase 3 and randomized to placebo
- Patients with prior participation in 402-C-1603 phase 3 and randomized to bardoxolone methyl
- Patients with prior participation in 402-C-1808 phase 3 and randomized to placebo
- Patients with prior participation in 402-C-1808 phase 3 and randomized to bardoxolone methyl
- Patients completed study when the study was terminated
- Continuing (or complete) treatment
- Terminate early from the treatment
  - Reason for terminating treatment
  - Terminated early from the treatment due to COVID-19
- Continuing (or complete) study
- Terminate early from the study
  - Reason for terminating study
  - Terminated early from the study due to COVID-19
  - Study week at study termination
  - Terminated prior to SDT
  - Terminated after SDT

Results will be summarized by analysis population (Section 6.3). A listing of disposition is provided for all patients.

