### 8.1. Adverse Event Preferred Term and Body/Organ System Summary Tables

Adverse events are summarized by treatment as defined by the safety analysis set. General considerations for AE summaries and calculations are:

- Multiple events by PT and SOC are counted once only per patient for summaries of AE incidence.
- For summaries of AE incidence by severity, only the most severe event is counted per patient.
- For summaries of AE incidence by relationship, only the most related event is counted per patient.
- An AE with a missing resolution date or incomplete date that is not identified as continuing is assumed to be continuing and no duration is calculated.
- Only TEAEs are included in summaries.

Adverse events are coded using MedDRA version 21.1. In MedDRA, each verbatim term is mapped to a PT and high-level term, which is then mapped to an SOC. Tables and listings will present data at the SOC and PT level.

Treatment emergent adverse events (TEAEs) are events that either:

- Have a date of onset on or after the date of the first dose in the 402-C-1803 study and not more than 30 days after the date of the last dose of study drug in the 402-C-1803 study, or
- Have no recorded date of onset with a stop date after the first dose of study drug, or
- Have no recorded date of onset or stop date

Adverse events with a date of onset in a prior study that continued during the 402-C-1803 study are not considered TEAEs.

In addition, AEs that occurred >30 days after the date of last dose of study drug are summarized as late-onset AEs. These are AEs that had a date of onset more than 30 days after the date of the last dose of study drug in 402-C-1803 study.

The investigator grades the severity of the AEs as mild, moderate, or severe as defined in the study protocol Section 11.5. The investigators graded association or relatedness to the study medication according to criteria specified in Section 11.4 of the study protocol.

As defined in the protocol, an SAE is an AE that results in any of the following:

- Death;
- A life-threatening adverse drug experience;
- Patient reaches ESKD (defined as the initiation of maintenance dialysis for 12 weeks or more or kidney transplant)
- Inpatient hospitalization or prolongation of existing hospitalization;
- Results in persistent or significant incapacity or substantial disruption of the ability to conduct normal life functions;

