### **8.1.2. Summaries of Adverse Events**

For each treatment analysis group, SOC, and PT, the number and percentage of patients reporting an event is calculated. In summary tables, SOC is presented alphabetically and events within SOC are presented by decreasing frequency count.

Summary tables (number and percentage of patients and events) of AEs (by SOC and PT) are provided by treatment analysis group as follows:

- All TEAEs
- All treatment-emergent related AEs (definitely, probably, or possibly related)
- All TEAEs by severity
- All treatment-emergent SAEs (including deaths)
- All related treatment-emergent SAEs (including deaths)
- All TEAEs leading to permanent discontinuation of study drug

Listings are provided showing:

- All AEs
- SAEs (including deaths)
- AEs leading to permanent discontinuation of study drug

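### Read as written, the SAP 6.6.3 rule for adverse events with a missing start day fails on-treatment events from an earlier year whose calendar month is later than the cut-off month.

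*SAP*

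**What the plan says.** SAP 6.6.3 defines a treatment-emergent AE (TEAE) mainly by its onset: on or after first dose and "not more than 30 days after the date of the last dose of study drug". It then gives rules for incomplete start dates, one set for the first-dose end of the window and one for the last-dose end.

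At the last-dose end there are three bullets. Call last dose plus 30 days the cut-off.

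- Day and month missing: "Day and month are missing, and the year is equal to or before the year of the date of last dose of study drug" (the SAP adds the 30 days here too). No month test applies.
- Day missing: the year must be no later than the cut-off year, "and month is equal to or before the month of the date of last dose of study drug plus 30 days".
- Year missing: the event is accepted.

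At the first-dose end, 6.6.3 uses two separate bullets for a missing day. A later year passes on year alone, and the month is compared only when the years are equal. The medication rule in SAP 6.6.2 has the same structure, beginning with "Day is missing and the year is after the year of the first date of study drug administration".

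SAP 8.1 states "Only TEAEs are included in summaries" and adds that "AEs that occurred >30 days after the date of last dose of study drug are summarized as late-onset AEs". SAP 8.1.1 refers back to 6.6.3 for partial onset dates and adds nothing.

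**The concern.** The last-dose bullet for a missing day compares year and month separately and requires both to pass. Dates have to be compared by year first, and by month only if the years tie. As written, any event from an earlier year fails if its calendar month is later than the cut-off month, however long before last dose it began. Neither of the other two bullets accepts such an event, because its month and year are both known.

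Frequency of AEs and serious AEs is part of the primary endpoint (SAP 3.2.1). If the bullet is programmed literally, affected events leave the TEAE tables in SAP 8.1.2, including those for related, serious and treatment-discontinuing events. At this end of the window the error only removes on-treatment events, so it can only lower incidence. Which events go depends on the calendar month of last dose, which has no clinical meaning. An event that fails could also be misfiled in the late-onset summary if a program sends every event failing the upper limit there.

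**Working it through.** **Inputs.** The rule is from SAP 6.6.3. First patient first visit was March 2019 (SAP Technical Summary Report). The study drug termination (SDT) date was 10 May 2023 (SAP 2). Individual dosing dates are not given, so those below are assumptions. Last doses will vary, since SAP 7.1 includes a disposition category "Terminated prior to SDT".

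**The two rules.** Let Y and M be the recorded start year and month, and Yc and Mc the year and month of the cut-off.

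- As written: pass if Y ≤ Yc and M ≤ Mc.
- Year then month: pass if Y < Yc, or if Y = Yc and M ≤ Mc.

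**One event.** Last dose 10 May 2023 gives a cut-off of 9 June 2023, so Yc = 2023 and Mc = 6. For an onset of November 2021:

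- As written: 2021 ≤ 2023 is true and 11 ≤ 6 is false, so it fails.
- Year then month: 2021 < 2023, so it passes.
- Recorded only as 2021: the bullet for day and month missing applies, 2021 ≤ 2023, so it passes.

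Whatever the missing day, November 2021 is before the upper limit in the TEAE definition. The rule therefore contradicts the definition it serves, and it keeps the less complete record while rejecting the more complete one.

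**Share of onset months that fail.** All calendar months from first dose to the cut-off month are counted. Each earlier calendar year contributes its months later than Mc. For March 2019 to 10 May 2023 the total is 10 + 36 + 6 = 52. July to December fail in each of 2019 to 2022, so 4 × 6 = 24.

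| First dose | Last dose | Cut-off month | Months failing as written |
|---|---|---|---|
| March 2019 | 10 May 2023 | June 2023 | 24/52 (46%) |
| January 2022 | 10 May 2023 | June 2023 | 6/18 (33%) |
| January 2023 | 10 May 2023 | June 2023 | 0/6 |
| January 2020 | 10 January 2022 | February 2022 | 20/26 (77%) |
| January 2020 | 10 May 2022 | June 2022 | 12/30 (40%) |
| January 2020 | 10 September 2022 | October 2022 | 4/34 (12%) |
| January 2020 | 10 November 2022 | December 2022 | 0/36 |
| January 2020 | 10 December 2022 | January 2023 | 33/37 (89%) |

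Nothing is lost when dosing plus 30 days stays within one calendar year or when the cut-off falls in December. The loss is near its worst when the cut-off falls in January. Under the year-then-month rule, the first row becomes 0/52 and the last 0/37. That rule also passes no month after the cut-off month.

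**The case against.** The literal reading is hard to dispute, so the case on the other side concerns consequence.

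- **The bullets say if, not only if.** No sentence declares an unmatched event non-treatment-emergent, and the TEAE definition alone would classify a November 2021 onset correctly. This does not rescue the text. These bullets are the only stated test for partial dates at the upper limit, and SAP 8.1.1 sends the programmer to them.
- **The intent is plain from the sibling rules, and a programmer may code it properly.** That is likely to be the intent. But the code would then depart from the written plan, and SAP 2 says the study report will describe such deviations.
- **A 2021 onset cannot meet the late-onset definition.** This stands. Misfiling needs a further coding step that the SAP does not state, so it is a possibility only.
- **The percentages are shares of months on chosen dates.** This also stands. They show how far the rule reaches, not how many events are lost. Serious AEs must be reported within 24 hours of site awareness (protocol 11.7), so a missing day may be less common among them. No counts are given.
- **All analyses are descriptive, and the events remain visible.** True. No test or decision rule turns on this. SAP 8.1.2, under "Listings are provided showing", keeps all AEs and serious AEs in the listings. The frequency tables are nevertheless how this part of the primary endpoint is reported.

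**Conclusion.** The concern holds. The bullet is wrong as written: it contradicts the TEAE definition in its own section and departs from the structure of both parallel date rules. It affects only AEs with month and year known and day missing, in patients whose treatment plus 30 days spans more than one calendar year. Under the assumed dates, the share of onset months failing ranges from none to 89%, and is 46% for the longest span to the SDT date. The number of such AEs is unknown, so the effect on incidence cannot be estimated. The harm also depends on the rule being programmed literally. The correction should be made because the logical error is certain, it bears on AE frequency, and it is cheap to remove.

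**What to change.** Replace the second last-dose bullet in SAP 6.6.3 with two that mirror the first-dose rule, where the cut-off is last dose plus 30 days:

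- Start day missing, and the start year is earlier than the cut-off year.
- Start day missing, the start year is the cut-off year, and the start month is no later than the cut-off month.

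Leave the other two bullets as they are. The cost is one bullet becoming two and, if the rule was coded literally, one changed line in the TEAE derivation. No new data are needed.
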